1.1 Background and Significance

Recurrent malignant pleural effusion (MPE) is a debilitating condition, which is associated with a significant morbidity and worsening of quality of life (QOL). Overall median survival of patients with MPE is poor and it changes slightly by histology: breast cancer, 7.4 months; non-small cell lung cancer, 4.3 months; and ovarian cancer, 9.4 months (1). Therapy of MPE is symptomatic and palliative, and consists of mechanical evacuation of the effusion to relieve pulmonary compression and dyspnea. There are no well-established methods of therapy, and the techniques used vary. They include repeated thoracentesis with small-bore catheters, tube thoracostomy, or video-assisted thoracic surgery for optimal drainage. Pleurodesis may be induced chemically by talc, tetracycline, doxycycline, bleomycin, or instillation of talc slurry(1). Patient selection is required since these techniques may be associated with complications (2). Several studies examined the utility of intrapleural drug administration for management of MPE. In a randomized trial, methylprednisolone did not delay reaccumulation of symptomatic pleural effusion compared to placebo (3). Immunotherapy with OK-432 had been shown to be feasible and active for MPE in a small-randomized trial (4). Recently a chronic indwelling pleural catheter has been introduced for the therapy of MPE. A randomized study examined its safety and efficacy versus tube thoracostomy and doxycycline sclerosis(5). Outpatient treatment with indwelling pleural catheter was found to be safe and equivalent in efficacy to treatment with tube thoracostomy(5). In addition, it was associated with fewer hospitalization days and was less expensive than inpatient methods(6). Our common practice in recent years had been placement of the indwelling pleural catheter in all patients who had reaccumulation of symptomatic malignant pleural effusion.

Tumor-Initiating Cells (TICs) in MPE

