In an IRB-approved laboratory study we cultured pleural effusion cells as spheres in tumor-initiating culture conditions (17, 18) and completed fresh flow cytometry analysis of the percentage of CD44+CD24-/lo epithelial cells (detected as CD45-CD326+ CD44+CD24-/lo cells) from 29 unselected patients with metastatic breast cancer who underwent pleurocentesis for symptomatic pleural effusion (Figure 1). In this exploratory analysis, we retrospectively examined the association between TICs and overall survival from the time of pleurocentesis and report that patients with higher percentages of TICs in the pleural fluid had significantly shorter overall survival than those with fewer TICs.

We analyzed fresh MPE samples from 29 pts with breast cancer for epithelial cells with a tumor-initiating cell phenotype (TIC, CD45-CD326+ CD44+CD24-/lo): CD45- (leukocyte

marker), CD326+ (also known as EpCAM an epithelial marker), and CD44+ and CD24-/lo (tumor-initiating markers), using multicolor flow cytometry on an IRB-approved protocol. Overall survival (OS) was measured from time of MPE assessment. Univariate analyses of survival were performed using Cox proportional hazards (CPH), with 1-year levels computed using the method of Kaplan-Meier. Multivariate analyses were performed using the CPH model. Median follow-up was 4.1 months, range 0.2 to 28.9. Eighteen patients have died of disease. Median percentage of CD45-CD326+ cells was 1.24% which contained a median TIC component of 9.5%. On univariate analysis, higher level of %TICs were significantly associated with differences in overall survival (Figure 2, $P = 0.005$). Actuarial 1-yr OS was 24% vs. 77% for patients with %TIC above (TIChi) and below (TIClo) the median ($P = 0.016$). Increasing percentage of TICs remained a significant predictor for worse OS on multivariate analysis (hazard ratio 1.25, confidence interval 1.06-1.49, $P = 0.007$). An increased percentage of TICs predicted for decreased OS among patients with MPE consistent with the hypothesis that these cells mediate recurrence and death from breast cancer.

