3.4 On-Study Evaluations

On the day of indwelling intrapleural catheter placement the patient's pleural fluid will be drained, recorded and sent for cytology review. On the day of indwelling intrapleural catheter placement patients will receive VPA or **placebo** if cytology is positive. Patients will be provided a diary to record drainage from home.

Patients will be treated for the whole period of 10 weeks, and clinical course of disease will be monitored throughout this time. (Note: evaluations may be done within \pm 7 business days of the date specified in the protocol).

Patients will initially receive daily oral VPA 15 mg/kg/day divided in three doses or placebo divided in three doses. Based on the patient's bmi, obese patient dosing will be based on the adjusted body weight calculated using the MD Anderson Clinical

Calculator Formula (<http://inside2.mdanderson.org/apps/calculators/calc1.cfm>). If the patient tolerates the reduced dose for 10 consecutive days then the VPA dose will increase to 30 mg/kg/day divided into three doses or placebo divided into three doses. The patient will be contacted by phone to assess tolerance and instruction to increase dose. Daily dose in mg will be divided by 250 mg and rounded down to a whole number of capsules to determine the number of VPA tablets or placebo tablets to be taken 3 times per day.

Evaluations may occur any time during weeks 2, 6, and 10.

- 3.4.1 Patients will document daily amount of pleural fluid drainage.
- 3.4.2 Patients will be evaluated at weeks 2, 6, and 10 with complete interim histories and physical examinations including measurement of vital signs, performance status, weight and medical history.
- 3.4.3 Patients will complete a EQ-5D and St. George's respiratory questionnaire, at weeks 2, 6, and 10 in person, via telephone or electronic media.
- 3.4.4 Blood samples for CBC with differential, platelet count, and PT/PTT/INR, serum and plasma banking, and optional CTC (if patient agrees) assessment will be collected prior to treatment and at weeks 2, 6 and 10.
- 3.4.5 Tests to measure serum electrolytes, BUN, creatinine, glucose, albumin, alkaline phosphatase, AST or ALT, LDH, total bilirubin, amylase, lipase, magnesium and ionized calcium will be performed at weeks 2, 6, and 10.
- 3.4.6 Optional urine (if patient agrees) will be collected prior to treatment and at weeks 2, 6 and 10.
- 3.4.7 Chest x-ray will be performed immediately after catheter placement and at weeks 2, 6, and 10.

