- 3.4.8 CT scan will be performed at week 10 or earlier, if clinically indicated, to determine amount of effusion and drug effect on tumor burden.
- 3.4.9 Pleural effusion will be collected at each clinic visit. Residual fluid may be stored for additional research studies (optional).

On-Study Evaluations beyond Week 10

The EQ-5D, St. George's respiratory questionnaire and the obtaining of pleural fluid samples for research purposes will cease at the end of Week 10. After the completion of 10 weeks of VPA or placebo the patient's medical record will be followed for the date of catheter removal or date of death, which ever comes first.

Study Parameters

Studies	Prior to catheter placement	Within 72 hours prior to catheter placement	Day of catheter placement	Weeks 2, 6 and 10*	Week 10	Review EMR
Physical Exam including: v/s, wt	X ³			X ³		
Medical History	X			X		
Pregnancy Test if applicable	X ^{1,3}					
Ionized Calcium	X ³					
Magnesium	X ³					
Bloodwork	X ^{2,3}			X ^{2,3}		
ECOG PS	X			X		
St. George's questionnaire	X ³			X ³		
EQ-5D	X ³			X ³		
CXR PA and LAT		X	X	X		
Patient daily documentation of pleural fluid drainage			X	X		
Patient daily documentation of VPA or placebo administration			X	X		
optional pleural fluid			X	X		
optional blood			X	X		
optional urine			X	X		
CT chest	X ⁴				X	
Serum valproic acid for grade 2 or greater AEs ⁵						
Date of pleural catheter removal or death date						X

- Serum or Urine Pregnancy test:** Required for females of child-bearing potential. Documented use of contraception, sexual abstinence, or amenorrhea for > 6 months is sufficient to document patient is not of child-bearing potential. Otherwise must be obtained prior to first dose of VPA and must be negative to enroll.
- Hematology: CBC with differential Chemistry:** Electrolytes, BUN, creatinine, glucose, albumin, alkaline phosphatase, ALT or AST, LDH, total bilirubin, amylase, lipase, magnesium and ionized calcium.
Coagulation: Prothrombin time (PT), partial thromboplastin time (PTT), and International Normalized Ratio (INR) at baseline only.
- Within 7 days of enrollment
- Baseline CT chest completed after development of effusion and within 4 weeks of enrollment.
- Draw serum valproic acid level for any grade 2 or greater adverse events.
- Evaluations may occur any time during weeks 2, 6, and 10.

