Operating Characteristics of Toxicity Monitoring Rule					
Rate of Toxicity Leading to Dose Reduction	Probability of Stopping Early	Sample Size			
		P_{25}	P_{50}	P_{75}	
0.20	0.020	40	40	40	
0.25	0.071	40	40	40	
0.30	0.205	40	40	40	
0.35	0.407	20	40	40	
0.40	0.636	15	30	40	
0.45	0.827	10	20	35	

Analysis

We will use summary statistics to describe the demographic and clinical characteristics of patients on each treatment arm.

Primary Outcome

Time to catheter removal will be measured from the date of placement of the catheter to the date it is removed. Removal of the catheter because it is no longer needed to drain the pleura will be considered an event. Removal of the catheter for other reasons will be considered competing risks. Patients who die before their catheter is removed will be considered censored on the date of death. We will use the methods described by Gooley et al. (1999) to estimate the cumulative distribution of time to catheter removal stratified by treatment arm and randomization strata.

We will use Cox (1972) proportional hazards regression to model time to catheter removal as a function of treatment arm, cytology, and lung re-expansion, as well as other potential prognostic factors, including ECOG performance status, the number of circulating tumor cells in the peripheral blood and in the pleural effusion.

Secondary Outcomes

We will use summary statistics to describe the amount of pleural fluid drainage by treatment arm, and we will use a two-sample t-test to compare treatment arms with respect to the mean amount of pleural fluid drainage. If the usual normality assumptions do not hold we will use the Mann-Whitney test to compare treatment arms with respect to the median amount of pleural fluid drainage.

We will compare treatment arms with respect to tumor burden using a Cochran-Mantel-Haenszel chi-square test stratified by concomitant therapy. Tumor burden will be assessed with chest cat scan during week 10.

We will use summary statistics to describe symptom burden dyspnea and exercise tolerance changes and dyspnea as measured by the EQ-5D and St George's respiratory questionnaire at baseline and again at weeks 2, 6, and 10. We will use repeated measures analysis of variance methods to assess differences between treatment arms with respect to QOL, dyspnea and exercise tolerance

Toxicity

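### Quality of life and dyspnoea are compared by an unspecified repeated-measures ANOVA, with no baseline adjustment, randomisation strata, or handling of missing and post-death scores

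*Combined protocol and SAP*

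**What the plan says.** Section 6.0, Secondary Outcomes, gives the between-arm comparison one sentence: "We will use repeated measures analysis of variance methods to assess differences between treatment arms with respect to QOL, dyspnea and exercise tolerance". The sentence before it promises summary statistics for these measures "as measured by the EQ-5D and St George's respiratory questionnaire at baseline and again at weeks 2, 6, and 10". Baseline is mentioned there, among the descriptive statistics. The ANOVA sentence names no time points, covariance structure, covariates or missing-data rule.

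Section 3.4.3 schedules the questionnaires "at weeks 2, 6, and 10 in person, via telephone or electronic media", and later in Section 3.4 the plan states: "The EQ-5D, St. George's respiratory questionnaire and the obtaining of pleural fluid samples for research purposes will cease at the end of Week 10".

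Randomisation is stratified by lung re-expansion (two levels) and ECOG performance status (0-1, 2, 3). Neither factor appears in this analysis, although the Cox paragraph for the primary outcome lists both as model terms.

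On survival, Section 1.1 gives a median of "breast cancer, 7.4 months" for malignant effusion. For the authors' own 29 patients it reports: "Actuarial 1-yr OS was 24% vs. 77% for patients with %TIC above (TIChi) and below (TIClo) the median". No section states an expected mortality at week 10.

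**The concern.** Symptom burden and dyspnoea are a declared aim (Section 2.1) and secondary objective (2.3.4) of a palliative trial. Patients may have ECOG status up to 3 and must have had at least one line of chemotherapy for metastatic disease. Scores will be missing because patients die or become too ill, so the missing values are unlikely to resemble the observed ones.

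Classical repeated-measures ANOVA needs a score at every visit. Run that way, it compares only patients who survived to week 10 with all scores. This loses precision and can bias the arm difference in either direction.

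Other routes to missing scores exist. Section 7.1 counts a treatment failure (infection, intractable pain, blockage and others) as completion of the study. Section 7.0 removes patients for intercurrent illness or inability to comply. Section 7.2 replaces dropouts without saying whether the scores they already gave are analysed.

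Baseline score is usually the strongest predictor of a later score, and the plan assigns it no role in the comparison.

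**Working it through.** The plan states no week-10 mortality, missing-data rate or power for these outcomes, so there is no figure of its own to reproduce.

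**Deaths by week 10**

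Inputs: 76 patients (Section 6.0); median survival 7.4 months and one-year survival of 24% and 77% in the two halves of the 29-patient cohort (Section 1.1); horizon 70 days = 70/30.44 = 2.30 months.

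- Constant hazard, 7.4-month median: 1 − 0.5^(2.30/7.4) = 19.4%. The same formula gives 4.2% at week 2 and 12.1% at week 6.
- Cohort, constant hazard within each half: 1 − 0.24^(2.30/12) = 23.9% and 1 − 0.77^(2.30/12) = 4.9%, mean 14.4%. Averaging the one-year survival first (50.5%) gives 1 − 0.505^(2.30/12) = 12.3%.
- Weibull with the 7.4-month median and shape k: 1 − 0.5^((2.30/7.4)^k) gives 26% at k = 0.7 and 6% at k = 2.

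**Complete cases if deaths are the only loss**

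- 76 × (1 − 0.194) = 61.3; 76 × (1 − 0.144) = 65.1; 76 × (1 − 0.123) = 66.7. In whole patients, 61 to 66.
- If a further 10% of survivors miss a visit (an assumption with no anchor in the documents), the ends become 61.3 × 0.9 = 55.1 and 66.7 × 0.9 = 60.0.
- A mixed model keeps partial records. At the 19.4% figure, patients dying between weeks 2 and 10 number about 76 × (0.194 − 0.042) = 11.6, and most could contribute at least one post-baseline score.

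**Cost in precision**

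For a simple two-sample comparison at two-sided 0.05, the standardised difference detectable with 80% power is (1.96 + 0.84) × √(2/n).

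- n = 38 per arm: 0.64.
- n = 30.6 per arm (19.4% lost): 0.72. Power at 0.64 falls from 80% to 71%.

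**Role of baseline**

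Suppose the effect is δ at weeks 2, 6 and 10 and zero at baseline. An arm main effect over four levels estimates (0 + δ + δ + δ)/4 = 0.75δ.

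Illustration, all inputs assumed: 38 per arm, δ = 0.5 SD, equal correlation ρ = 0.5 between visits. The variance of a mean of k visits is (1 + (k − 1)ρ)/k, and baseline adjustment subtracts ρ². Power is Φ(effect/√(2v/38) − 1.96).

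| Analysis | Effect | v | Power |
|---|---|---|---|
| Four levels including baseline, arm main effect | 0.375 | 0.625 | 54% |
| Three post-baseline visits, unadjusted | 0.5 | 0.667 | 76% |
| Three post-baseline visits, baseline as covariate | 0.5 | 0.417 | 92% |

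With ρ = 0.3 the three powers are 66%, 85% and 90% (90.5% before rounding); with ρ = 0.7 they are 46%, 68% and 97% (97.5% before rounding). The ordering does not depend on the chosen correlation.

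**The case against.** The strongest reply is that the plan commits none of these errors in words. A reader might infer that it drops patients with any missing visit. No section sets such a rule, and the plural 'methods' could cover a likelihood-based model that keeps partial records. A reader might also infer that baseline is analysed as an outcome. Baseline is named only in the descriptive sentence, so a covariate, a change score or an outcome level all remain possible. Even with baseline as a level, an arm-by-visit test would use within-patient change and escape the 75% dilution. These replies stand, and both consequences are therefore stated conditionally.

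Missingness among survivors may also be modest. Telephone and electronic completion are allowed, visit windows are wide, and Section 7.0 keeps patients on scheduled procedures when treatment stops early for safety. That also stands, but it does nothing about death, and it does not clearly cover patients classed as treatment failures.

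The gain from baseline adjustment depends on the comparator. Against an unadjusted single post-treatment score, the variance falls by r², or 25% at r = 0.5 and 49% at r = 0.7. Against a change score, it falls by (1 − r)/2, or 25% and 15%. No single percentage can be claimed while the planned contrast is unknown.

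Finally, a mixed model does not by itself resolve truncation by death, because it implicitly models scores that a dead patient could not have given. This is correct and shapes the fix.

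**Conclusion.** The point holds as a weakness in the named analysis with a better method available on the same data. Nothing in the plan adjusts these comparisons for baseline or the strata, or says what happens to missing and post-death scores. The classical form of the named method would lose every patient without a full set of visits.

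Deaths alone would account for roughly 12% to 19%, or about 9 to 15 of 76 patients. A reader might take one death in five by week 10 as the plan's expectation. The plan states no such figure: 19.4% requires a constant hazard applied to a median quoted from the literature, and the authors' own cohort points to about 12% to 14%. Varying only the hazard shape gives 6% to 26%. The power figures are illustrations under assumed effects and correlations.

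The direction of any bias is unknown. These are secondary outcomes with no power claim and no role in stopping, and the primary result is unaffected.

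**What to change.** Replace the ANOVA sentence with a likelihood-based mixed model for repeated measures on the scores at weeks 2, 6 and 10. Include arm, visit, arm-by-visit, baseline score, lung re-expansion and ECOG stratum, and use every patient with a baseline and at least one post-baseline score.

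Add three items:

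- the estimand with respect to death: either while alive, or a composite in which death counts as an outcome;
- a table of deaths by arm and visit beside the score comparison;
- one sensitivity analysis that allows scores to be missing not at random.

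This applies directly to the EQ-5D and St George's scores. The six-minute walk test named in Section 2.1 has no visit in the Section 3.4 schedule, so the same model can be used for it only if it is collected.

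The cost is a change of SAP wording, to be made before unblinding, and a little more analysis work. No new questionnaire data, visits or patients are needed.

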5.1.6 Concomitant Treatment

Use of VPA at this dose has been documented in patients receiving FEC chemotherapy and is routinely used as an anti-seizure medication among breast cancer patients receiving chemotherapy for metastatic disease. Patients currently receiving hormonal or systemic chemotherapy for metastatic disease will be eligible. Toxicity will be assessed after half of the accrual is met, and early stopping rules will be employed.

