5.3.1.1 Guidance for all other Adverse Events

Figure 5. Non AST, Non ALT, Non Amylase, Non Lipase And Non CNS Adverse Event (All other adverse events) Management
Study drug dosing is for 10 total weeks. During treatment visits will correspond to the week the patient is actively administering drug.

[figure not shown]

Figure 6. Grade 3 Non CNS Adverse Event Management Not assessed under Figure 4
Study drug dosing is for 10 total weeks. During treatment visits will correspond to the week the patient is actively administering drug.

[figure not shown]

Figure 7. Any Grade 2 deemed NOT possibly related to other systemic treatment

[figure not shown]

Figure 8. CNS Adverse Event Management NOT related to study drug (possible, probable or definite attribution)
Study drug dosing is for 10 total weeks. During treatment visits will correspond to the week the patient is actively administering drug.

[figure not shown]
[figure not shown]

Figure 9. Grade 3 Non CNS Adverse Event Management Possibly related to study drug and Possibly related to other oncologic systemic treatment
Study drug dosing is for 10 total weeks. During treatment visits will correspond to the week the patient is actively administering drug.

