Patients will be randomized to active treatment or control stratified by lung re-expansion ($\geq 80\%$ lung re-expansion, $<80\%$ lung re-expansion), ECOG performance status (0-1, 2, 3), using the Clinical Trial Conduct website (<https://biostatsitics.mdanderson.org/ClinicalTrialConduct>), which is housed on a secure server at MDACC and maintained by the MDACC Department of Biostatistics. Access to the website will be gained through usernames and passwords provided by the MDACC Department of Biostatistics to personnel responsible for enrolling patients and reviewing and analyzing patient data. Training on the use of the Clinical Trial Conduct website to randomize and enroll patients on the study will be provided by the study statistician. Investigation Pharmacy will have access the Clinical Trial Conduct website

to review the patient assignment. The IND office will be notified if an event occurs leading to the un-blinding of the randomization.

Toxicity Monitoring

We will use the methods described by Thall et al. (1995) to monitor the rate of toxicity leading to dose reduction for patients on active treatment. Because the study is blinded to the investigators, the study statistician will monitor the toxicity monitoring rule for the active treatment arm. Toxicity data leading to dose reduction will be forwarded to the study statistician as they accrue in the form of an email with the patient study identifier and a description of the toxicity leading to dose reduction.

If the rate of toxicity leading to dose reduction for patients on active treatment is more than 25% the study will be stopped. We will enroll a minimum of 10 and a maximum of 40 patients on active treatment. We will stop the study early if $P(\text{toxicity leading to dose reduction for patient on active treatment} > 25\% | \text{data from the study}) > 0.975$. That is, given the toxicity outcomes from the patients on active treatment, if we determine that there is more than a 97.5% chance that the rate of toxicity leading to dose reduction is more than 25% we will stop the study. This decision rule gives the following stopping rule. We assume a uniform prior distribution for the rate of toxicity leading to dose-reduction. Stop the study if

[# of pts on active treatment with toxicity leading to dose reduction / # of pts evaluated]
> 6/10, 8/15, 9/20, 11/25, 13/30, 14/35, 16/40

The operating characteristics of this study design are shown in the table below.

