We will estimate the rate of toxicity leading to dose reduction for patients on the active treatment with a 90% credible interval. If we have toxicity leading to dose reduction in 5 of the 40 patients on the active treatment, then our 90% credible interval for the rate of toxicity leading to dose reduction will be 6.6% to 23.6%. We will also report the posterior probability that the rate of toxicity leading to dose reduction for patients on the

active treatment is more than 25%.

We will tabulate adverse events by treatment arm, grade, and relationship to study drug.

Translational Studies

For CTC studies using the adnagen approach .3 ng/ml in GA733-2 or muc-1 will be considered positive and both conversion to negative and change from baseline (using continuous data) will be assessed. Descriptive statistics will be applied. Using the Veridex system 5 CTCs will be considered positive for all dichotomous analyses and conversion to negative and change from baseline will be assessed as above.

Statistically significant conversion to negative in the VPA arm in either test will be considered a significant change. CTC studies will be performed only if funds are available and will be done by [name] who has extensive experience with both tests.

For quiescence and stem cell analysis flow cytometry will be performed for cell cycle, CD44+CD24-CD45-Epcam+ and aldefluor. Samples will be divided into three replicates to address run variability. Total percent quiescent (G1/G0) epithelial cells will be the primary metric for correlative evaluation although quiescence within stem cell populations will be assessed and reported. All data are continuous variables.

Dichotomous analysis will be based on values > or <= to the median for the entire dataset for each variable. All biomarker analyses related to outcome will be performed according to REMARK guidelines incorporating time to metastases, extent of metastatic disease (multiple vs. effusion only), triple negative vs. not, extent of prior therapy, and KPS. Analysis will include correlation between percent quiescent cells and time to catheter removal in both arms and change in percent quiescent cells from baseline in both arms. Given there will be significant variation in the baseline G0/G1 measurement we will consider a 30% relative increase in G0/G1 from baseline significant.

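### Toxicity leading to dose reduction is monitored and estimated in the valproate arm only, so the planned summary cannot separate added from background dose reductions

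*Combined protocol and SAP*

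**What the plan says.** Section 6.0, Toxicity Monitoring, sets a fixed ceiling: "If the rate of toxicity leading to dose reduction for patients on active treatment is more than 25% the study will be stopped". It is applied through a posterior probability, stopping when there is "more than a 97.5% chance that the rate of toxicity leading to dose reduction is more than 25% we will stop the study". The prior is stated: "We assume a uniform prior distribution for the rate of toxicity leading to dose-reduction". So is the number monitored: "We will enroll a minimum of 10 and a maximum of 40 patients on active treatment". Because the investigators are blinded, "the study statistician will monitor the toxicity monitoring rule for the active treatment arm". Dose-reduction toxicities reach the statistician by e-mail under the patient's study identifier, and no restriction to one arm is stated.

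Section 6.0, Toxicity, plans the final estimate in the same way: "We will estimate the rate of toxicity leading to dose reduction for patients on the active treatment with a 90% credible interval". It adds the posterior probability that the active-arm rate exceeds 25%, and a table of adverse events by arm, grade and relationship to study drug.

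Section 5.1.6 allows background treatment: "Patients currently receiving hormonal or systemic chemotherapy for metastatic disease will be eligible". Section 5.1.4 names bone marrow suppression as the primary toxicity when 30 mg/kg/day was given with chemotherapy. Section 5.3.1.1 expects events of mixed origin; the title of Figure 9 is "Grade 3 Non CNS Adverse Event Management Possibly related to study drug and Possibly related to other oncologic systemic treatment". The Sample Size text in Section 6.0 plans 38 patients per arm.

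**The concern.** The monitored event is any toxicity leading to dose reduction. Section 6.0 does not limit it to toxicity attributed to valproate, and the patients may be receiving drugs with overlapping toxicity. The active-arm rate is then a gross rate: valproate plus background. A single-arm trial has nothing better, but this trial has a concurrent randomized placebo arm in which the same event can be counted.

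Two things are at stake. In the final report, the same active-arm figure could reflect a large valproate effect or none, and the planned summary would look identical. In monitoring, a stop could be triggered partly by background toxicity, and nothing in the plan would show the statistician's audience that placebo patients were being reduced as often.

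**Working it through.** **Inputs from Section 6.0.** Uniform prior, threshold 25%, posterior cut-off 0.975, boundaries 6/10, 8/15, 9/20, 11/25, 13/30, 14/35 and 16/40, and 38 patients per arm. The background rate is not in the documents. It is an assumption here, shown as a range.

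**Step 1: reproduce the plan's figures.** With x events in n patients the posterior is Beta(1+x, 1+n-x).

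- *Credible interval.* For 5/40, Beta(6, 36) has 5th and 95th percentiles 6.57% and 23.95%. The plan prints 6.6% and 23.6%. The upper limit is about 0.3 points off, which does not affect this point.
- *Boundaries.* All seven are the smallest x with P(rate > 25%) > 0.975. For example, 6/10 gives 0.992 and 5/10 gives 0.966; 16/40 gives 0.985 and 15/40 gives 0.967.
- *Stopping probabilities.* I used an exact sequential binomial calculation, stopping when the count reaches the boundary. The printed sign before the boundaries is a strict inequality, but the posterior rule and the printed table both need reached or exceeded. Six looks (10 to 35) match the table within 1 point; a seventh look at 40 raises the values slightly.

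| True active-arm rate | Plan's table | Six looks | Seven looks |
|---|---|---|---|
| 0.15 | not given | 0.003 | 0.003 |
| 0.20 | 0.020 | 0.019 | 0.019 |
| 0.25 | 0.071 | 0.075 | 0.078 |
| 0.30 | 0.205 | 0.204 | 0.217 |
| 0.35 | 0.407 | 0.407 | 0.435 |
| 0.40 | 0.636 | 0.635 | 0.671 |

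**Step 2: what the rule does if valproate adds nothing.** Both arms then share the background rate, and the table is read with that rate in the first column. Stopping is rare at 15% or 20%, is about 0.08 at 25%, and becomes material from about 25-30% upward.

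**Step 3: background added to a valproate effect.** Assume that valproate alone causes 15% dose reductions and that the causes act independently. The active-arm rate is 1 - (1 - b)(1 - 0.15) for background b.

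| Background b | Active-arm rate | P(stop), six to seven looks |
|---|---|---|
| 0% | 15.0% | 0.003 |
| 10% | 23.5% | 0.05 |
| 15% | 27.8% | 0.14 |
| 20% | 32.0% | 0.28-0.30 |
| 25% | 36.3% | 0.46-0.50 |

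**Step 4: the final estimate.** The counts are illustrations. For 8/38 on active, Beta(9, 31) gives 12.6% to 34.0% and P(rate > 25%) = 0.33. This output does not depend on placebo. The difference between two independent Beta posteriors does:

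| Active | Placebo | 90% interval for difference (points) | P(active > placebo) |
|---|---|---|---|
| 8/38 | 2/38 | +2.6 to +27.9 | 0.98 |
| 8/38 | 8/38 | -15.2 to +15.2 | 0.50 |
| 5/40 | 0/40 | +3.1 to +22.1 | 0.99 |
| 5/40 | 5/40 | -12.4 to +12.4 | 0.50 |

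The planned summary is the same in rows 1 and 2, and again in rows 3 and 4, although the conclusions about valproate differ.

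**Step 5: precision.** With 38 per arm, a two-sided 5% comparison of proportions has about 40% power for 10% against 25%, and about 75% for 10% against 35%.

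**The case against.** The strongest reply has four parts.

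- **Attribution may filter the background.** Section 5.2 assigns attribution by clinical judgment, lets a high serum valproate level inform it (and unblind the patient), and the titles of Figures 7 to 9 separate study drug from other systemic treatment. This stands in part: some chemotherapy toxicity may never cause a reduction of study drug. The flowcharts are not shown, so the amount cannot be checked. For the same reason, a reader might infer from the title of Figure 9 that blinded staff must be reducing placebo for chemotherapy toxicity; the documents do not establish that. Equally, they do not show that the filter removes the background.
- **Adverse events are tabulated by arm.** This stands. A reader might infer that the trial has no means at all of telling added from background toxicity; that goes too far, because the table is a planned descriptive comparison. It is organized by grade and relationship, however, and does not give the placebo rate of toxicity leading to dose reduction.
- **An absolute ceiling can be deliberate caution.** This stands. It limits what patients on valproate plus background treatment actually experience, and preferring a comparative rule is a design choice. The point here is the missing comparator, not the ceiling.
- **The comparison would be imprecise.** This stands too. With about 10 per arm at the first look, the placebo count is mostly noise.

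**Conclusion.** The point holds as a gap in estimation and reporting. The stopping rule, the credible interval and the posterior probability use the active arm only, and no placebo rate, difference or ratio of the same event is planned. For the illustrative 8/38, the unreported difference could be centered near zero or lie between +2.6 and +27.9 points. This part needs no high background rate.

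The monitoring half is weaker. A reader might infer that background chemotherapy toxicity is likely to stop the trial. The documents do not support that, because they give no background rate. If valproate adds nothing, the stopping probability is about 0.003 at 15%, 0.02 at 20%, 0.08 at 25%, 0.20-0.22 at 30%, 0.41-0.43 at 35% and 0.64-0.67 at 40%. Background alone matters only at about 25-30% or more, though lower rates matter when added to a valproate effect.

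These results rest on the uniform prior, on boundaries read as reached or exceeded, on independent arms, and on assumed background rates and counts. The primary endpoint is not affected. This is a cheap improvement.

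**What to change.** In Section 6.0, Toxicity, add that the final analysis will report the rate of toxicity leading to dose reduction with a 90% credible interval in each arm, the difference with its 90% credible interval, and P(active rate > placebo rate), using the same uniform prior.

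In Toxicity Monitoring, add that the study statistician, who already uses assignments to apply the rule, will list the placebo count beside the active count with any stop recommendation.

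The active-arm 25% rule is unchanged, so this informs a stop but does not prevent one.

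The cost is a few sentences and a few more numbers. No new data are needed, because the e-mailed reports carry patient identifiers and are not described as limited to one arm. The text should say that the comparison is imprecise with 38 per arm, especially at early looks, so that a small placebo count is not over-read.
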